The remaining measures for treatment adherence (i.e., Homework Compliance Scale and Psychosocial Compliance Scale), as well as measures for app acceptability (i.e., Subjective App Usability Scale) and treatment acceptability (i.e., Subjective Treatment Acceptability) will be collected at the post-treatment assessment. Maintenance of treatment adherence will also be collected at the 3-month follow-up assessment. Treatments will be compared on these outcome measures using one-way analysis of variance (ANOVA).

- **Secondary analyses:** Treatment conditions will be compared using a general linear mixed modeling (GLMM) approach for secondary outcome variables (i.e., psychiatric functioning and psychosocial functioning) using IBM SPSS software. Time will be based on the standard interval assessments of the study – the baseline, post-treatment, and follow-up assessment). Time, treatment condition, and their interaction will be the primary predictors (controlling for any significant covariates). Psychiatric symptoms, psychosocial functioning, and emotion regulation (measured continuously) will be the outcome variables for these analyses.

We will also test a mediation analysis, with average participant adherence (measured throughout the study) as the mediator between treatment conditions and the secondary outcome variables. This will be done in two sets of analyses using the SPSS Process macros, which is a statistical package within SPSS that runs bootstrapped mediation analyses. First, the effect of treatment condition, mediated by average treatment adherence, on post-treatment psychiatric and psychosocial functioning will be examined. Second, the effect of treatment condition, mediated by average treatment adherence, on 3-month follow-up psychiatric and psychosocial functioning will be examined.

- **Exploratory analyses:** Two exploratory analyses will be examined. We will make use of the app's big data collection to begin to elucidate the app's effect on participant adherence and clinical outcomes.
 1. Using functional data analytic techniques, the uptake of that app will be examined. First, each of the components of participant adherence (skill-practice, symptom monitoring, and review of session content) will be examined to determine the functional pattern of participant adherence over time. This analysis will examine the trajectories of each component of participant adherence over the study to examine their function (i.e., increasing, decreasing, stable over time). Additionally, this analysis will determine which component of participant adherence had the highest frequency of practice.
 2. The frequency and duration of app use will be mapped across the study to determine how often and for how long participants engaged with the app. Additionally, the frequency and duration of app use will be moderated with time of reward reinforcement to determine if the use of the app was affected by the reward structures (e.g., leveling up, receipt of an emoji) within the app.

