research outreach programs. I have budgeted in salary support for a research coordinator two days per week throughout Years 1-4 of the award. The research coordinator will screen all interested participants by phone to assess study eligibility, explain the purpose of the study and study procedures, and answer any questions. For individuals interested and eligible in participating, youth will complete the informed assent process and their parent/guardian will complete the informed consent process (detailed below). In addition to the phone screening of eligibility criteria, an in-person eligibility assessment will be conducted with the PI and research coordinator to assess for DSM/SIPS diagnostic criteria, explain the study procedures in more detail, and answer any questions. Recruitment will be done until there are enough participants to randomize and fill two groups of $n > 6$ per group.

Overview of study activities: Aim 1 will consist of focus groups, followed by an iterative app-development process with an interdisciplinary expert panel, and then an open trial of an app-enhanced cognitive-behavioral treatment (CBT). Focus groups will be held in a conference room at the UCLA Semel Institute and last approximately 60 minutes. The open trial will consist of a pre-treatment assessment, nine 90-minute group treatment sessions, and post-treatment session that includes an exit interview. Aims 2 & 3 will consist of a RCT of the app-enhanced CBT, which will compare nine 90-minutes sessions of the group CBT to nine 90-minute sessions of the app-enhanced group CBT. The RCT will also consist of a pre-treatment assessment, a post-treatment assessment, and a 3-month follow-up assessment following the completion of the group. The open trial and the RCT will be held in group therapy rooms at the UCLA Semel Institute. Finally, I will conduct longitudinal and machine learning analyses of data collected throughout the RCT.

Study Procedures, Materials, and Potential Risks

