Participants may at times experience sadness or discomfort when discussing family issues, personal problems, or psychiatric symptoms, but no more than they would if they took part in psychotherapy or pharmacotherapy sessions in the community. Discussing psychiatric problems may at times be upsetting to the adolescent. If these reactions occur, the research staff, all of whom are well-trained and supervised by the PI (a licensed psychologist), will offer the participants emotional support and validation. Participants will also be informed that they can receive and follow-up on referrals for counseling outside of the study at any time.

The adolescents recruited for this study will meet criteria for a mood disorder and deemed at risk for a severe mood disorder. There is no reason to suspect that adverse events related to the illness (e.g., hospitalizations) will be higher if the adolescent receives treatment in the study instead of in a community treatment setting. In fact, because of the psychosocial protocols administered in this study, the increased availability of between-session communication with study staff, rates of adverse events may be lower than if patients were treated in the community. Nonetheless, we will track all adverse events – whether study related or not - using an Adverse Events Form previously developed for this age group and used in the primary mentor's family therapy trials.

ADEQUACY OF PROTECTION AGAINST RISKS

Training of Staff

All research staff proposed for the study have received human research ethics and HIPAA training. They will be trained in the study's recruitment and informed consent procedures before collecting any data for this study. The PI and primary mentor will develop a study procedures manual that clarifies how to explain the study to participants and parents and address questions about random assignment and other study-related matters. Training will require that study staff read through and discuss the manual and participate in role-plays of the recruitment and informed consent process (for example, how to determine if the proband and parents fully understand the protocol before signing informed consent or assent documents). The PI will supervise the recruitment of study participants, and will meet regularly with the primary mentor to review recruitment progress.

Referral to the Program

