Recruitment will start when an adolescent or their parent self-refers to the project or is referred by a treating physician or psychotherapist. When study candidates are referred by a mental health professional, this professional will give the participants a copy of an IRB-approved study flyer explaining the purposes and design of the study. The treating clinician can offer to contact the research team if the adolescent and at least one parent signs a HIPAA Authorization Form releasing their protected health information (names, diagnosis, ages, address, and telephone number) to the research team. This release will enable the team to contact the participants to determine their eligibility. A copy of the signed authorization form will be provided to the participants and placed in their medical chart. Alternatively, many families prefer to make the initial contact themselves rather than have their physician make the contact.

Telephone Screening, Informed Consent and Screening Visit

After referral to the program, the project coordinator will initiate a telephone interview of one or both parents of the adolescent. The coordinator will ask the parent to clarify the adolescent's reasons for referral to the program. If the adolescent and parents are interested and the adolescent appears eligible, they are invited to conduct a baseline eligibility assessment.

The initial baseline visit is intended for the adolescent and his or her primary caregiver(s). During this visit, we will obtain information on the presence of mood symptoms in the past month, past and current diagnoses and treatment for a psychiatric disorder and current medications and psychosocial treatments (if any). The project coordinator will explain the study protocol, answers all questions, and conducts the a semi-structured interview to determine eligibility. If the candidate is eligible, and the candidate and family wish to proceed, the project coordinator explains the written consent/assent documents to the parent(s) and adolescent. The coordinator will explain that, if the adolescent meets eligibility criteria the study offers treatment through a randomly assigned protocol involving either family psychoeducation and skills training or family psychoeducation and supportive individual treatment.

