Once the parents and youth have signed the consent and assent forms, a trained research diagnostician (independent evaluator) will administer the Structured Clinical Interview for DSM-5 (SCID-5 Research Version; First et al., 2015). This interview and scale ratings are conducted separately with the adolescent and at least one parent, with the adolescent's diagnostic consensus ratings based on both reports. When necessary, these interviews can be spread over two appointments.

In the event that there are unanswered questions about eligibility (e.g., whether the adolescent has regularly abused substances in the past 6 months), additional interviews with the adolescent and parent may be required. After reviewing the baseline assessments, the study staff and PI will meet to determine eligibility. Feedback will be provided to the family regardless of whether the adolescent meets eligibility criteria for the study. All subjects will receive copies of the signed consent or assent documents, HIPAA authorization forms and 'The Experimental Subject's Bill of Rights'.

Informed Consent and Assent

Upon meeting study criteria, youth participants will be assented and their parent/guardian will be consented in person. Prior to consent, the PI will explain study procedures in detail, discuss potential risks and benefits of participation, remind them that the study is voluntary and their choice to participate will not impact the care they receive. They will be informed that they can choose to withdraw freely and may also choose not to answer any questions. They will get the PI's contact information as well as UCLA's IRB contact information if they have additional questions or concerns. The PI will assess patients' understanding of the study and study procedures and will provide them with a copy of their signed consent form to keep. Study consent forms will be kept separately from study data and will be locked in a filing cabinet within the PI's research office. We will submit for approval of all study procedures and protocol to the UCLA IRB prior to initiating any study activity.

Limits to Confidentiality

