This study proposes to recruit a relatively young (ages 13-17) sample. If the researchers have reasonable cause to believe that child abuse or neglect is occurring, or there are circumstances which might result in child abuse or neglect, they will comply with California state laws by filing a child abuse report with the Department of Child and Family Services. If the research staff believe that a participant is at risk of harming someone else, they are required to take necessary actions. These actions include notifying the parent of the participant's intentions, notifying others who might be affected (i.e., intended victims), or notifying the police or the Department of Child Services. In these cases, the research staff will be unable to preserve the participant's confidentiality. These limits to confidentiality will be spelled out in the participants' consent and assent forms. We will notify parents if we learn that an adolescent participant is actively abusing alcohol or drugs in a way that is life-threatening or otherwise a danger to him- or herself or others. If an adolescent participant has experimented with a drug or alcohol on a single occasion, notifying the parents may not be indicated. Nonetheless, it will be necessary to monitor this behavior in family or individual support sessions. If we disclose these behaviors to parents, we will meet with the family to help resolve family conflicts and introduce preventative measures. Additional counseling sessions beyond the required number will be tabulated and included as covariates in the treatment/outcome analyses.

Protections Against Risk

Data safety will be maintained to the most rigorous standards as detailed above. Survey responses will be entered into Chorus. Electronic and audio data will be stored within the UCLA Health System's encrypted firewall, will be password protected, and protected by anti-virus software. Any hard copies of participants' data will only contain a unique study ID and stored in a locked filing cabinet within the PI's office. All study codes (including a link between participant names and identifying information) will be kept in a password-protected electronic file on a secure server. Password access will be limited to the PI and to any individuals that are IRB

approved for this study. All study links between participant IDs, names, and identifying information will be destroyed when the study has ended. Approval of all study documents will go through UCLA's IRB.

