treatment, is based on the premise that participants need to practice the skills in order to improve. Since participants commonly forget to do the skills, lose their homework assignments, or feel unmotivated to complete the skills, it challenges treatment developers to improve the current treatments and address these barriers to patient compliance. **We propose using a mobile app to improve patient compliance for youth at risk for SMD.** A mobile app can remind participants of skills they need to practice, provide the psychoeducation and skill-practice within the app, and provide contingencies that reward and increase motivation for skill-practice. Additionally, the large amounts of data that a mobile app collects allows for advanced statistical techniques, such as machine learning, to be applied. These efforts can provide a wide range of benefits to youth at risk for SMD and clinical science more broadly. Improving patient compliance can improve treatment outcomes, which reduces burdens on families who face these psychiatric challenges and society at-large who faces this emotional and financial burden. Additionally, through use of machine learning, we can better determine who will and who is benefitting from a skills-based treatment, like CBT. This prediction can help us better tailor treatment recommendations for patients and determine which patients will or will not benefit from a particular type of treatment.

STATISICAL DESIGN AND POWER

Power calculations

For this pilot RCT, we plan to randomize 60 participants to the randomized controlled-trial of the mobile-enhanced treatment. The two treatment groups will be randomized in a 1:1 ratio. Based on pilot trials of this treatment group as well as my primary mentor's ([name]) previous work with interventions for adolescents at high risk for SMI, we anticipate no more than 15-20% dropout by the end of the six-month study. Thus, we expect a final sample size of about 50 with full follow-up (25 in each treatment condition) across 3 assessment time-points (baseline, post-treatment, and three-month follow-up). Actual power will be higher as our general linear mixed modeling allows inclusion of data from subjects with partial data.

Additionally, data collected via the mobile application (app) should greatly increase the number of measurements.

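### The explanation planned for the consent visit names two randomised treatments, neither of which is an arm of this trial

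*Combined protocol and SAP*

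**What the plan says.** Under Telephone Screening, Informed Consent and Screening Visit, once a candidate is found eligible and the family wishes to go on, "the project coordinator explains the written consent/assent documents to the parent(s) and adolescent". The next sentence gives the content of that explanation on random assignment: the study offers treatment through "a randomly assigned protocol involving either family psychoeducation and skills training or family psychoeducation and supportive individual treatment". The paragraph after that begins at the point where the forms have been signed.

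The paragraph headed Overview of study activities describes a different RCT, "which will compare nine 90-minutes sessions of the group CBT to nine 90-minute sessions of the app-enhanced group CBT". The section on power calculations matches it: "we plan to randomize 60 participants to the randomized controlled-trial of the mobile-enhanced treatment", and "The two treatment groups will be randomized in a 1:1 ratio".

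Two other passages bear on what families are told. Under Informed Consent and Assent, "Prior to consent, the PI will explain study procedures in detail". Under Training of Staff, the PI and primary mentor will "develop a study procedures manual that clarifies how to explain the study to participants and parents".

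**The concern.** The sentence is current protocol text and states what a member of staff will say. It is not background. It comes during the explanation of the consent and assent documents, when a family is deciding whether to accept randomisation.

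What is being randomised is central to informed consent, and here the decision is made for adolescents aged 13 to 17 with mood disorders. A family that hears this sentence is led to expect family psychoeducation in either arm and, in one of them, individual supportive treatment. The trial delivers neither as a randomised treatment. The sentence also leaves out the app, the only difference between the two real arms, and the group setting, although the section on potential risks lists discomfort in a group and with audio-recording among the risks.

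**Working it through.** No arithmetic applies. The point depends on no alpha, power, effect size or rate. The check is to compare every description of the randomised treatments.

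| Feature | Consent-visit explanation | Overview of study activities |
|---|---|---|
| First arm | Family psychoeducation plus skills training | Group CBT, nine sessions of 90 minutes |
| Second arm | Family psychoeducation plus individual supportive treatment | App-enhanced group CBT, nine sessions of 90 minutes |
| Format | Family, with individual treatment in one arm | Group in both arms |
| What separates the arms | Skills training or supportive treatment | The app |

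1. **Do the arms match under any pairing?** No. Skills training could loosely describe CBT, but it is attached to family psychoeducation, which neither real arm contains. Individual supportive treatment corresponds to neither real arm. The app does not appear. The number of arms matching is 0 of 2.

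2. **Which account does the rest of the document support?** The title and the opening overview describe a mobile- or app-enhanced treatment. The benefits section refers to participants who receive the app-enhanced treatment. The power section randomises 60 participants, 1:1, in a trial of the mobile-enhanced treatment. All fit the overview of study activities. None fits the consent-visit sentence.

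3. **Does family or individual contact appear elsewhere as a treatment arm?** No. Limits to Confidentiality says of a single episode of substance use that "it will be necessary to monitor this behavior in family or individual support sessions", and Addressing Clinical Emergencies describes extra meetings and family work when suicide risk is judged low. These are support or crisis measures. The first also sits awkwardly with a group CBT design, which suggests, without proving, that some wording was carried over from a family-therapy protocol.

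4. **Does another step correct the sentence on paper?** No. The PI's explanation before consent is described without naming the arms. The procedures manual has still to be developed, and its content is not given. The phone screen, the in-person eligibility assessment and the flyer are all said to explain the study, but none is said to name the two arms.

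**The case against.** The strongest reply is that this sentence is one of several contacts before consent. The coordinator explains purpose and procedures by phone, and the PI and coordinator explain them again in person. At the consent visit the coordinator also explains the protocol and answers questions, so the disputed sentence is not the whole account. The PI then explains procedures and assesses understanding. Families referred by a professional receive an IRB-approved flyer on the design. Ability to attend group sessions and access to a smartphone are inclusion criteria, so most families would probably meet the group format and the app before they heard the sentence.

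Much of this stands, and it limits the consequence. A reader might infer that families would consent to the wrong treatments. The documents do not support that: the sentence accompanies written forms that are not included and may be correct. A reader might also infer that families would learn nothing of the group format or the app before signing. That is not established either.

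A third tempting inference is that misinformed families would leave and push dropout above the assumed 15-20%, or weaken the adherence outcome. The documents give no basis for any count of such families. Those who refuse before randomisation are not among the 60 and are not dropouts. The same explanation precedes allocation in both arms, so no route to a difference between arms is shown.

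None of this removes the contradiction. At best, families would hear a correct account and an incorrect one.

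**Conclusion.** The protocol is wrong as written on this point and must be corrected. The planned oral explanation before signing describes two randomised treatments, and neither is in the trial. Confidence in the contradiction is high: the text is current, the two descriptions cannot be read as variants of each other, and no other section reconciles them.

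The consequence is conditional. If the sentence is followed, it would misdescribe the randomised treatments to the parents and minors who hear it. That rests on staff using the text uncorrected, and the written forms or the PI's own explanation might put it right. The case for correction rests on accurate consent for minors alone. There is no effect on sample size or power, and any effect on dropout or adherence cannot be quantified from the documents.

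**What to change.** Replace the sentence in Telephone Screening, Informed Consent and Screening Visit with the two arms given in the overview of study activities. State that treatment in both arms is delivered in groups, and name the app with its voice-journal data collection, which the Data Monitoring section describes.

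Before any RCT family is approached, check the flyer, the procedures manual and the consent and assent forms for the same wording. The manual matters because staff are to rehearse the consent process from it. Review the reference to family or individual support sessions under Limits to Confidentiality at the same time, so that it is reconciled with the design.

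The cost is a protocol text correction and notification of the IRB. Budget, sample size and analysis are unaffected.
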